All participants will be assigned a unique reference number which will be linked to personal details stored securely on paper. Any electronic data will be anonymous, bearing the unique reference number of the participant and their initials only, with no personally identifiable information included within the data files. Only the CI will have the ability access to trace data files created from accelerometry measurements to the individual participant, using their unique reference number and initials within the file name.

Any paper documentation, which may include personal data (e.g. signed consent form, personal contact details), will be kept in a locked filing cabinet within the Therapies Centre, Hull Royal Infirmary. This is shared with one other colleague, [name], who is also a member of the PhD supervision team. This office is always locked when vacant. Preferred personal contact details will only be obtained at the consent phase should the participants express a desire to hear of the results.

The CI will adhere to the NHS Information Governance (IG) Toolkit Regulations, professional codes of conduct and relevant HEYHT and YSJU policies and procedures at all times. No information regarding research participants will be passed to third parties not directly involved in the research.

The identity of individual participants in the research report and any publications will remain confidential and anonymous. Data protection will conform to the Data Protection Act 1998.

Finance

This study has not received any funding from external sponsors and all accelerometry equipment and software has been supplied by YSJU. Lack of an ability to employ language interpreters, due to no external funding has necessitated the requirement to enrol only those who have a good command of the English language.

Reporting and dissemination

This study will form part of a PhD thesis, investigating the validity of a particular model of accelerometer (the Actigraph GT3X) for use as a clinical measurement tool to quantify the typical activities patients undertake on a hospital ward as they continue their recovery following critical illness.

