The inconsistency of correct determination of body position of this accelerometer model when worn around the waist has been demonstrated by other authors (Berendsen et al., 2014, Hänggi et al., 2013). The inconsistency of correct identification of the sitting position in particular was highlighted by (Hänggi et al., 2013). Other researchers have investigated ways of improving the ability to correctly classify the sitting position (Skotte et al., 2014). The study by (Skotte et al., 2014)

determined that the addition of a second Actigraph GT3X accelerometer placed on the mid-thigh yielded excellent results in detection of the sitting position. Pressure sensors in subjects' hip pockets were used as a criterion measure to classify body position.

As mentioned previously, the feasibility undertaken by the CI determined that the ankle placement was superior to the waist for recognition of step count. When walking a ten metre distance with a walking aid, using observed step count as a criterion measure the ankle placement demonstrated a mean difference -1 step, (Limits of Agreement (LOA) +3 to -5 steps) compared to the waist placement (mean difference -7 steps, LOA +9 to -23 steps). These positive findings for step count for the ankle placement are supported by a recent study cited earlier using a similar Actigraph model investigating the accuracy of step count in older adults (Korpan et al., 2015).

Defining the research question

Using the findings from the feasibility study regarding the ankle placement of the Actigraph GT3X accelerometer and the research cited suggesting improved classification of the sitting position with the addition of a thigh mounted accelerometer the following research question is proposed:

Can an Actigraph GT3X accelerometer, placed at the ankle and thigh of the same leg, accurately measure body position and walking episodes undertaken by patients recovering from critical illness in a hospital ward?

A number of study objectives evolve from this research question, assisting in the development of the methodological processes required to answer it.

1. To determine the criterion validity of the ActiGraph GT3X accelerometer in detection of body position and step count when positioned either on the mid-thigh or ankle of the same leg.
2. To establish if there is a superior single body placement site (thigh or ankle) to objectively record body position and step count within this patient population.

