3. To investigate the criterion validity of the combination of thigh and ankle accelerometer inclinometer outputs to correctly determine the sitting position. This

will determine whether an algorithm can be constructed using the two inclinometer readings, which will better distinguish the sitting from the standing position.

4. To evaluate, from a user perspective, the acceptability of these devices in relation to the placement sites used. This will be achieved by asking patients to score the answer to a particular question through the use of a Likert scale. The question is:
 - How would you rate the comfort of wearing the accelerometers?

In consideration of the results from the feasibility study undertaken by the CI and research using the addition of a thigh mounted accelerometer to identify the sitting position (Skotte et al., 2014), the following hypotheses can be constructed:

Hypotheses

1. An ankle mounted Actigraph GT3X accelerometer, will accurately identify both the lying and standing positions when compared with direct observation as a criterion measure.
2. An ankle mounted Actigraph GT3X accelerometer, will capture a step count comparable to that recorded by direct observation in a population resident on a hospital ward recovering from critical illness.
3. The combination of inclinometer outputs of both the thigh and ankle placement sites will permit development of an algorithm permitting the ability to better distinguish between the sitting and standing position.
4. The ankle and mid-thigh accelerometer placement sites will be well tolerated by patients recovering on a ward from critical illness.

Subject selection and involvement

The study will invite adult hospital ward patients recovering from critical illness to wear one Actigraph GT3X accelerometer on the antero-medial mid-thigh and another on the ankle, resting above the lateral malleolus of the same leg. The accelerometers will be worn for a period of time not exceeding three hours. Each device will be attached with a single patient use broad elastic belt, secured by Velcro fastening, using a standardised placement protocol. The non – dominant leg will be the preferred placement side.

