Following completion of the data collection period, the information captured by the accelerometers will be downloaded as soon as possible onto the laptop computer. The time when a movement commenced and ceased (with the addition of five seconds to accommodate accelerometer processing), will be noted by the CI. The type of movement and body positions adopted will also be documented (lying, sitting or standing). If the movement involves walking, the CI will count the number of steps undertaken manually, entering all of the above information onto a data collection sheet. The participant will not miss any refreshments, food or any investigations and they will also be encouraged to undertake usual daily activities, e.g. reading a paper or watching the television. If the participant requests some time alone, in the case of making a phone call for example, the CI will comply, but encourage the participant to remain in the same body position. If they were sitting in a chair for example, they would be encouraged to remain seated, agreeing a time for the CI to return (e.g. fifteen minutes). Should any procedures or personal cares be necessary, the CI will respect the need for privacy and dignity and leave until they are complete. The data captured by the accelerometers during these time periods will be excluded from data analysis, as there will be no criterion measure (observation) to compare accelerometer data against.

Observational data will be collected by the CI using a data collection form specifically designed for this purpose, which will be entered into an electronic format within the IBM SPSS statistics programme (version 20) for data analysis. The CI will undertake all data collection procedures and undertake statistical analysis.

Upon completion of the period of observation the accelerometers will be removed and the skin examined for one final time. Participants will be asked to rate their views on acceptability of wearing the accelerometers at the two placement sites. They will be asked to consider the question in relation to the individual placement sites and in combination. One question will be asked:

1. How would you rate the comfort of wearing the accelerometers?

[figure not shown]
Participants will be requested to match their answer to a statement on a five-point Likert Scale which will be printed on a sheet for them:

1. Very uncomfortable
2. Somewhat uncomfortable
3. Neither comfortable or uncomfortable
4. Somewhat comfortable

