Advice has been sought from the HEYHT Tissue Viability Team during construction of this methodological protocol. The inclusion and exclusion criteria have been constructed in such a way to consider those populations where placement of the accelerometers may pose additional and unnecessary risk. An assessment form has been constructed with advice from the same team to use when undertaking the half hourly assessment of skin integrity and circulation of participants during the data collection period. The Tissue viability team borrowed the accelerometers to assess whether they posed any significant risk to tissue viability and to assist in construction of the eligibility criteria for participation.

Data collection process

A data collection sheet will be populated during the data collection period. Rest periods and the positions participants adopt (e.g. lying, sitting or standing) will be recorded also.

Accelerometer data will be captured using the three different measurement modes available on the GT3X devices. Activity intensity detection is a default setting on the devices. These modes can be initialised onto the accelerometers simultaneously for eventual download onto the computer. A password protected laptop computer will be used for the initialisation of the accelerometers and subsequent data download. This laptop computer has direct remote access to the CI's personal folders on the York St John University (YSJU) virtual desktop facility, which is secure and password protected. Data files can be transferred electronically to the YSJU student virtual desktop to permit statistical analysis within SPSS.

The accelerometer settings (measurement modes) will be:

- Physical activity count (a default setting), giving a numerical score related to intensity of activity, the greater the count, the greater the acceleration of movement, hence the greater intensity
- Step count
- Inclinometer for identification of body position (lying, sitting or standing)

There are only four readings the inclinometer setting on this particular device can supply, which are detailed below:

0 = Device is off (not being worn by patient)

1 = standing

2 = lying horizontally

3 = sitting upright

Sample size calculation

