Percentage agreement of inclinometer raw data from the thigh and ankle accelerometers with direct observation for detection of each separate body position will be calculated. A further percentage agreement analysis will be undertaken if an algorithm can be constructed for determination of the sitting position using readings from both placement sites. This algorithm will be compared against direct observational raw data identifying the sitting position only. This result will be compared against the percentage agreement of the individual placement sites in determination of the sitting position. This will assist in determination of whether the algorithm is more superior to a single placement site in determination of the sitting position.

Continuous data

Agreement between step count recorded by each accelerometer placement site and direct observation (manual counts) as a criterion measure will be determined using Bland Altman analysis with 95% limits of agreement (LOA).

Acceptance of the devices over a three-hour period

The statements within the Likert scale will be collapsed to obtain true positives (very comfortable and somewhat comfortable) and true negatives (very uncomfortable and somewhat uncomfortable). The middle category (neither comfortable nor uncomfortable) will remain a separate category. A descriptive analysis will be undertaken to investigate this particular aspect of enquiry using percentages of true positives, the middle category and true negatives. This will be presented graphically.

Any specific comments made by the patients in relation to acceptability of the devices will be included as free text within the results section. The statements will be anonymous and permission from participants will be sought regarding their inclusion within the body of the thesis or publications which may arise from it.

Ethics approval

This study has received approval from the NHS Local Research Ethics Committee (REF: XXXXX) and the Research Ethics Sub Committee, YSJU (REF: XXXXXX).

Data handling and confidentiality

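### The question is about walking episodes, but the only walking analysis is step-count agreement with no stated unit, so false steps may be left out or offset missed steps, and missed bouts are not separately identified

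*Combined protocol and SAP*

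**What the plan says.** The section 'Defining the research question' asks whether accelerometers at the ankle and thigh can "accurately measure body position and walking episodes undertaken by patients recovering from critical illness in a hospital ward". The objectives that follow replace walking episodes with step count: objective 1 concerns criterion validity for body position and step count, and objective 2 asks for the better single site for the same two measures. Hypothesis 2 states that the ankle device "will capture a step count comparable to that recorded by direct observation in a population resident on a hospital ward recovering from critical illness".

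Under 'Study procedure' the criterion is conditional on walking: "If the movement involves walking, the CI will count the number of steps undertaken manually". Under 'Statistical analysis', 'Continuous data', the whole walking analysis is: "Agreement between step count recorded by each accelerometer placement site and direct observation (manual counts) as a criterion measure will be determined using Bland Altman". Limits of agreement are to be given at the 95% level. No unit of comparison (walk, participant or session) is given. The kappa and percentage-agreement analyses under 'Categorical data' use lying, sitting and standing, with no walking class.

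The data needed to look further are already planned. Devices record in one-second epochs. On timing, the plan says: "The time when a movement commenced and ceased (with the addition of five seconds to accommodate accelerometer processing), will be noted by the CI". The 'Data collection process' section adds: "Rest periods and the positions participants adopt (e.g. lying, sitting or standing) will be recorded also".

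**The concern.** A device that measures walking episodes must register steps when the patient walks and must not register them otherwise. The plan reports neither property separately. The movement protocol includes turning onto each side, moving from lying to sitting over the bed edge, and standing up. All of these move the leg that carries both sensors.

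The background section on the accelerometer describes the hoped-for use as unobtrusive monitoring through the day, including finding patients who are inactive although able to move. There, nobody marks for the device when a walk starts and stops. Steps registered in bed or chair would make an inactive patient look active.

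Objective 2 is exposed as well. If ankle and thigh differ in the steps they register during transfers, a site comparison confined to walks would not show it.

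**Working it through.** **1. The plan's own figures.** The feasibility study, in healthy volunteers, reported an ankle mean difference of -1 step with limits +3 to -5 over a ten-metre walk with an aid. The midpoint is (3 - 5)/2 = -1, as stated. The implied SD is (3 + 5)/(2 × 1.96) = 2.04 steps. The plan gives no figure for missed bouts, for steps outside walking, or for walking time.

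**2. Two readings of the unit.**
- *Within walks.* This is the only precedent in the documents: the feasibility study counted steps during the walking activities and reported agreement over a fixed walk.
- *Session totals.* Nothing in the 'Continuous data' section rules this out.

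**3. Illustration.** Assumed: 3 bouts of 20 steps per participant; error in a detected bout with mean -1 and SD 2.04 (from step 1); a missed bout scores -20; false steps outside walks are Poisson with mean 6 per session; independence throughout.

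Per bout, with 10% of bouts missed:
- bias = 0.9 × (-1) + 0.1 × (-20) = -2.9
- variance = 0.9 × (2.04² + 1²) + 0.1 × 20² - 2.9² = 4.65 + 40 - 8.41 = 36.24, so SD = 6.0

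Session totals:
- no errors of either kind: bias 3 × (-1) = -3.0; SD √(3 × 2.04²) = 3.5
- 10% missed only: bias 3 × (-2.9) = -8.7; SD √(3 × 36.24) = 10.4
- 6 false steps only: bias -3.0 + 6 = +3.0; SD √(12.48 + 6) = 4.3
- both: bias -8.7 + 6 = -2.7; SD √(108.7 + 6) = 10.7

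| Bouts missed | Mean false steps | Within walks: bias, SD | Session total: bias, SD |
|---|---|---|---|
| 0% | 0 | -1.0, 2.0 | -3.0, 3.5 |
| 10% | 0 | -2.9, 6.0 | -8.7, 10.4 |
| 0% | 6 | -1.0, 2.0 | +3.0, 4.3 |
| 10% | 6 | -2.9, 6.0 | -2.7, 10.7 |

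A simulation of 20 participants per study agrees; the average sample SD in the last cell was 10.5.

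**4. Reading the table.** Within walks, the rows with and without false steps are identical: false steps are invisible at any rate. Missed bouts are visible as a larger bias and SD, but mixed with ordinary miscounting. With totals, the last row has almost the same bias as the error-free row. Its limits are much wider, but do not show which error widened them.

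**5. What 20 participants could show.** Assuming one bout each, exact 95% intervals for the proportion of bouts detected are 83-100% for 20/20, 68-99% for 18/20 and 56-94% for 16/20. More bouts per participant add information, but they are clustered within participant.

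**The case against.** The strongest defence is that the plan is internally consistent. The document says its objectives evolve from the research question; objectives 1 and 2 and hypothesis 2 specify step count, and the analysis matches them. All-day unobserved monitoring is described only as something the device could permit, not as an objective. This stands as far as it goes: the step-count analysis is a legitimate scope. But a conclusion would then have to be confined to step count, and the question as posed, about walking episodes, would be answered only in part.

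A reader might infer that missed walking bouts are never evaluated. The documents do not support that. A wholly missed bout enters a per-bout comparison as minus its full observed count, and it lowers a session total. The defect is that it is not identified as a missed bout.

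A reader might also infer that false steps are certainly excluded. That depends on the unit, which the plan leaves open.

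A reader might want a percentage error from false steps. Walking time, cadence and false-step rate would all have to be assumed, three hours is a maximum, and unobserved periods are excluded from analysis. Any such figure would only restate its inputs.

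Finally, second-by-second sensitivity and specificity look like the natural remedy but do not suit these data. At an assumed 50 steps per minute, at most 50 of 60 one-second epochs can hold a step, so a perfect step counter reaches at most 50/60 = 83%. An assumed 20-step walk at that pace lasts 24 s, so the five seconds added to recorded times are 5/24 = 21% of it.

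**Conclusion.** The concern holds in limited form. The research question names walking episodes; the analysis covers step-count agreement only, with a criterion that exists only during walking and an undefined unit. Neither bout detection nor steps registered outside walking is reported separately. False steps are left out under one reading of the unit and can offset missed steps under the other.

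The size cannot be established from the documents. The figures above show the mechanism and rest on the assumed bout number, bout length, missed-bout rate and false-step rate, with an error SD borrowed from healthy volunteers. That the two errors are not separated depends on none of those values.

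This does not invalidate the planned Bland-Altman analysis. It limits what can be concluded about walking episodes, and it leaves the choice of site under objective 2 possibly resting on walk windows alone. Because the data are already planned, this is a worthwhile and inexpensive improvement.

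**What to change.** In 'Statistical analysis', 'Continuous data', add for each placement site:

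- **(a) Unit.** State that step-count agreement is computed per observed walking bout, define a bout (including whether steps taken while turning or transferring count as walking), and allow for several bouts per participant.
- **(b) Bout detection.** Report the proportion of observed walking bouts in which the device registers steps.
- **(c) Steps outside walking.** Report device steps per hour in observed non-walking time, split into lying, sitting, standing where available, and postural transfers. Standing may be sparse, since quiet standing is not a separate item of the movement protocol. State in advance how the five seconds added to recorded times are handled at the edges of a walk. Exclude unobserved periods, as the plan already does.

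Summarise (b) and (c) by participant and present them descriptively. Use them together with the limits of agreement when naming the better site under objective 2.

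No new data collection is needed: the one-second epochs, start and stop times, positions and rest periods are already planned. The cost is a few sentences and some extra tabulation. The limitation is precision, as the intervals will be wide with 20 participants, and the results cover observed time only.

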Body mass index (BMI) will be calculated by using the latest weight recording (in kilogrammes) on the participants observation charts and asking participants to estimate their height, which will be converted to centimetres if given in feet and inches. Participants will wear two Actigraph GT3X accelerometers, one anteromedially around the mid - thigh and the other around the ankle of the same (ipsilateral) leg resting above the lateral malleolus. The CI will attach the accelerometers, ensuring they feel comfortable and pose no circulatory concerns. The placement sites will be checked on a half hourly basis during the data collection period. This has been recommended by the tissue viability team, to ensure the accelerometers are not compromising skin integrity or circulation. A standardised assessment form will be used for this process, which has been constructed with assistance from the tissue viability team.

The data collection period will not exceed three hours; including rest periods. Accelerometers will be removed at any time during the data collection period should a participant request this. Any data that has been collected during the time period that the accelerometers were worn prior to the request for removal will be downloaded and included within the analysis with the participant's permission.

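### Hypothesis 4 claims good tolerability, but the skin and circulation findings recorded for every participant enter no analysis, and no recorded skin baseline is described

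*Combined protocol and SAP*

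**What the plan says.** Four places in the combined protocol and SAP bear on this point.

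- **Objective and hypothesis.** Objective 4 (Defining the research question) is "To evaluate, from a user perspective, the acceptability of these devices in relation to the placement sites used", to be met with one Likert question about comfort. Hypothesis 4 (Hypotheses) reads "The ankle and mid-thigh accelerometer placement sites will be well tolerated by patients recovering on a ward from critical illness". Neither gives a definition or threshold for being well tolerated.
- **Checks during wear.** Under Study procedure, "The placement sites will be checked on a half hourly basis during the data collection period". The stated purpose is "to ensure the accelerometers are not compromising skin integrity or circulation", and "A standardised assessment form will be used for this process". Tissue viability considerations describes the same form as being for the "half hourly assessment of skin integrity and circulation of participants during the data collection period".
- **Checks at the two ends.** When fitting the devices, the chief investigator makes sure they are comfortable and raise no circulation concern (Study procedure). At the end of observation, "the accelerometers will be removed and the skin examined for one final time".
- **Analysis.** Under Acceptance of the devices over a three-hour period, "A descriptive analysis will be undertaken to investigate this particular aspect of enquiry using percentages of true positives, the middle category and true negatives". Participants' comments on acceptability are reported as free text. The Statistical analysis section does not mention skin or circulation results.

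**The concern.** Compromised skin or circulation under the belts is the hazard that the protocol sets out to monitor, and it monitors it in everyone. Good tolerability would ordinarily be read as covering that hazard as well as comfort. As planned, the evidence set against Hypothesis 4 is what participants say about comfort. A belt that felt comfortable but left a mark would produce the same planned result as one that left no mark.

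A second gap follows from the first. If the skin findings were reported, they would need a starting point. Participants have been ventilated for more than 48 hours in intensive care, so some may already have marks on the leg (an assumption, since the documents give no rate). No skin record before attachment is described, and one cannot be recovered later.

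At stake is how far the study can support, or has to limit, its own tolerability statement.

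**Working it through.** The plan states no figure on this point, so there is nothing to reproduce. The check compares the text section by section and then asks what 20 participants could show.

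**1. What is collected and what is analysed**

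| Information | Where collected | Planned analysis |
|---|---|---|
| Comfort rating, by site and combined | Study procedure | Percentages in three categories |
| Participants' comments | Study procedure | Free text |
| Half-hourly skin and circulation form | Study procedure; Tissue viability considerations | None described |
| Skin examination at removal | Study procedure | None described |

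**2. What is known before the first half-hourly check**

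- Before the session (Recruitment of study participants): ability to do the movements and absence of deterioration are confirmed. Skin is not mentioned.
- At fitting (Study procedure): comfort and circulation are checked. A skin examination or a recorded result is not mentioned.
- A finding absent at one check and present at a later one can be dated to the wear period. The ambiguous case is a skin mark already visible at the first half-hourly check.

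**3. Volume of data**

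A full 180-minute session gives at most 5 checks in session (30, 60, 90, 120 and 150 minutes) plus 1 at removal, so 6. Over 2 sites and 20 participants the ceiling is 6 × 2 × 20 = 240 site-assessments. Sessions may be shorter, and repeated checks on one person are not independent. The sensible unit is therefore the participant, per site: any new finding, yes or no.

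**4. What N = 20 could show**

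N = 20 comes from Sample size calculation. The intervals are exact (Clopper-Pearson) and the event counts are illustrative.

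- 0 of 20: upper limit of the two-sided 95% interval = 1 − 0.025^(1/20) = 16.8%.
- 1 of 20: 5% (95% CI 0.1% to 24.9%).
- 2 of 20: 10% (95% CI 1.2% to 31.7%).
- One pre-existing mark wrongly counted as new moves the observed rate by 1/20 = 5 percentage points.

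The chance of seeing at least one affected participant is 1 − (1 − p)^20:

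| Assumed true rate p | Chance of at least one in 20 |
|---|---|
| 2% | 33% |
| 5% | 64% |
| 10% | 88% |
| 15% | 96% |

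The study could therefore be expected to reveal a common problem but could not exclude an uncommon one. If attrition left only 12 assessable participants (the number the cited sample size calculation called for), 0 of 12 would give an upper limit of 1 − 0.025^(1/12) = 26.5%.

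**The case against.** The strongest reply is that Objective 4 is expressly about the user's view, and that the comfort question and its analysis match it. On that reading the skin checks are a participant safeguard advised by the tissue viability team, not an endpoint, and Hypothesis 4 is merely loosely worded. This has force: objective, question and analysis do agree with each other. It does not remove the mismatch with the wider claim in Hypothesis 4, but it makes narrowing that hypothesis a legitimate remedy.

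It is also fair to say that tolerability is a descriptive aim within a validity study, that wear lasts three hours at most, and that the kappa, percentage-agreement and Bland-Altman results do not depend on it.

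A reader might infer more than the documents support:

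- *That nothing is checked before or at attachment.* Comfort and circulation are checked at fitting, and peripheral vascular disease is an exclusion. What is not described is a recorded skin baseline. The form is not reproduced, so it may contain one.
- *That the hypothesis rests on comfort ratings alone.* Free-text comments are reported too.
- *That a choice between ankle and thigh would be distorted.* Objective 2 selects a site on recording of body position and step count. No selection on tolerability is planned.
- *That the plan forces a favourable verdict.* The analysis is descriptive, with no decision rule.
- *That no later finding could be attributed to the device.* Serial checks identify changes that appear after the first one.

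**Conclusion.** The point holds as a modest gap. Hypothesis 4 claims more than its planned analysis addresses, and the only objective tolerability data collected are left out of that analysis. In addition, no recorded skin baseline is described, which leaves marks present at the first half-hourly check uninterpretable.

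The size is limited. No stated figure changes and the validity objectives are untouched. With 20 participants a clean result would still be compatible with a true rate of up to 16.8%. The conclusion rests on two things that cannot be verified from the documents: that the unreproduced form has no pre-attachment entry, and that pre-existing marks occur often enough to matter. If the form does have such an entry, the baseline part falls away and the analysis part remains. This is a cheap improvement, not a flaw that undermines the study.

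**What to change.** 1. In Study procedure, have the existing assessment form completed for both sites immediately before the belts are attached. If the form already provides for this, say so.
2. Under Acceptance of the devices over a three-hour period, add beside the comfort percentages the number and percentage of participants with any new skin or circulation finding relative to that baseline, separately for ankle and thigh, with exact 95% confidence intervals. Count participants, not individual checks.
3. State that the conclusion on Hypothesis 4 draws on comfort and these findings together.

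If the team prefers not to treat the checks as an outcome, the alternative is to reword Hypothesis 4 as a statement about comfort or acceptability, in line with Objective 4.

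The cost of the first route is an estimated minute or two per participant, one descriptive table, and a tolerability result that may look less favourable. The baseline has to be in place before data collection. Rewording costs nothing in procedure, but gives up the wider claim.
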